Study Protocol

Official Title: Optimizing Care for Patients with Dementia: A Comparison of Two Non-Pharmacological Treatment Approaches

ClinicalTrials.gov ID (NCT number): NCT03442322

Protocol Date: December 2017, revised August 2021 due to COVID-19 pandemic

Scientific Background

More than half of the 1.4 million long-term care nursing home (NH) residents have a diagnosis of Alzheimer's Disease and Related Dementias (ADRD), which we will refer to as dementia throughout this report.¹ Residents living with dementia experience devastating negative effects associated with these progressive, irreversible conditions that result in loss of independence and subsequent long-term institutionalization. As the disease progresses, disruptions in the resident's daily routine, difficulty communicating personal needs, and environmental overstimulation or sensory deprivation often trigger the behavioral and psychological symptoms of dementia (e.g., agitation).²⁻⁴ If untreated, these symptoms result in negative side effects such as self-inflicted pain, limited food/liquid intake, accidental falls, and injuries to self or others (e.g., residents, NH staff), increasing the risk of hospitalization and death.⁴

In the early 2010s, more than 30% of NH residents were taking antipsychotic medication.⁵ To reduce this antipsychotic medication use in NH residents, the Centers for Medicare & Medicaid Services (CMS) championed a national initiative to enhance NH dementia care, starting in 2012. This comprehensive program, which had a goal of reducing national NH resident antipsychotic medication use, included NH staff and state surveyor training, established minimum standards for dementia care, and introduced a new quality measure (i.e., the percent of long-stay residents who received an antipsychotic medication) that all CMS certified NHs were mandated to report.⁶

Off-label antipsychotic medications, while commonly used to address the behavioral and psychological symptoms of dementia, have been shown to be ineffective and cause harm to the person living with dementia,⁷ including an elevated risk of death.⁸ By 2019, approximately 23% of NH residents living with dementia were administered off-label antipsychotics.^{5,9} However, these off-label medications have significant negative impacts on the resident's mortality and quality of life, primarily due to inducing withdrawal and lethargy.¹⁰⁻¹²

Given these poor outcomes, families, ADRD and resident advocates, and recent national initiatives have prioritized the reduction of antipsychotic medication use and shifted attention to increased use of non-pharmacological interventions in the NH context.^{6,13-15} In particular, CMS has recommended NHs reduce antipsychotic medication use to improve the quality of dementia care.⁶ Further, based on our preliminary data, family members and NH providers strongly support the use of non-pharmacological approaches for dementia care.

Common features of such approaches include training staff to understand the disease process of dementia and equip them with strategies to address triggers for negative resident behaviors, such as disruptions in routine or communication difficulties.¹⁵ Given the multi-faceted nature of triggers, evidence suggests that non-pharmacological treatments must incorporate a wide range of NH staff, such as professional healthcare providers and direct care providers.^{13,16} First, professional healthcare providers (e.g., include registered nurses, licensed practical nurses, social services, and rehabilitation practitioners/therapists) collaborate to develop a comprehensive, multi-dimensional plan of care to address factors that precipitate

behavioral and psychological symptoms of dementia (e.g., triggers). Second, NH direct care providers (e.g., certified nursing assistants [CNAs], dietary staff, social services, activities department staff), ancillary support staff (e.g., housekeeping), as well as family, are trained by the professional healthcare providers with strategies to support the customized plan of care.^{4,17} Collaboration across these individuals ensures maximum support to minimize episodes of extreme behavioral and psychological symptoms of dementia, thereby promoting optimal function, enhancing quality of life for the resident, and improving safety of all individuals.

Two leading approaches (*team- and problem-based*) to dementia care, prioritized by our community-partners, help staff implement non-pharmacological, resident-centered dementia care. Both approaches have randomized control trial (RCT)-level evidence to support efficacy and integration into clinical practice.^{4,11,18-23} The NHs using the *team-based (TB) approach to integrated dementia care* provide core training to all professional healthcare providers, direct care providers, ancillary support staff, and administrators, using a common language across disciplines to support continuity and sustainability. Results of randomized trials have indicated that the collaborative TB approach decreases the use of medications as well as the frequency and severity of resident agitation, pacing, and repetitive vocalization, compared to the minimum mandated usual care.^{19,24-26} In contrast, the multidisciplinary approach for *problem-based (PB) dementia care* draws on the expertise of the individual professional healthcare providers (e.g., speech language pathology, occupational therapy, nursing) to target issues that arise. For example, when residents have a change in status (e.g., weight loss, accidental fall event, change in self-care or mobility, emergence of behaviors during morning care routine), the nurses request a screen to be conducted by the relevant healthcare providers to determine the need for a resident evaluation by the respective discipline(s), revision to care plan, and treatment to address the emergent issue (i.e., change in status). These providers then train all other staff and family in resident-specific strategies and adjust the care plan as needed. In randomized trials, the PB approach has been found to decrease the frequency and severity of challenging behaviors (including aggression and calling out), as well as reduce the use of antipsychotic medications, when compared to usual care.^{25,27}

Despite evidence supporting TB and PB approaches to dementia care, clear gaps in evidence limiting implementation exist. Guided by our community-partners, our team identified the following gaps in evidence and variability in practice patterns that require urgent attention:

First, although efficacy studies support both approaches,^{4,11,18-23} the underlying studies have only compared the two approaches to individual, discipline-specific interventions or usual care.^{19,24,25,27} These two interventions have not been compared to each other; thus, it is not clear which approach is most effective given the varied resident and NH contexts across the US.

Second, prior studies have been limited by small samples of residents living with dementia (Ns=4 to 250) and use of researchers as opposed to NH personnel for intervention delivery.¹⁷⁻¹⁹ Although supportive of feasibility and general efficacy, previous studies have not provided professional healthcare providers, other NH staff, or NH administrators with the evidence to support widespread implementation, due to the above-noted problems.

Third, there is currently no standardized way in which professional healthcare providers and other NH staff communicate their efforts to ensure that residents living with dementia receive appropriate daily care. Although all NHs provide specialized services (e.g., occupational therapy, recreation therapy, nursing), few NHs support the coordination of care in a predetermined manner, resulting in NH staff often receiving training or information to support their interactions with a resident only after an incident of extreme behavioral and psychological symptoms of dementia occurs.

Although these care approaches are currently used in care delivery, there is significant variability in practical implementation. This variability is primarily due to wide differences in education and dementia-specific training across the numerous NH staff involved in dementia care. Efforts to minimize behavioral and psychological symptoms of dementia through non-pharmacological approaches must better account for the diverse education and training needs of the collective NH staff who all contribute to the care for residents on a day-to-day basis.

The COVID-19 pandemic altered NH care delivery and further exacerbated existing factors that contribute to aggression, agitation, and behavioral and psychological symptoms of dementia among residents. The pandemic policies put in place to minimize viral spread further perpetuated the challenges associated with caring for this vulnerable population.²⁸⁻³⁰ This new “normal” created a tension between life safety and an individual’s quality of life. For example, NHs had to restrict family visitation per CMS guidance, eliminate all resident group activities and congregate meals, and constrain resident access to limited areas of the NH campus to mitigate spread.^{31,32} These examples reflect disruptions in the resident’s routine and changes in the environment, all of which contributed to potential exacerbation of behavioral and psychological symptoms associated with dementia. As a result, these COVID-19 policies fostered social isolation and environmental under-stimulation among residents,³² increasing the likelihood of a resident living with dementia experiencing behavioral and psychological symptoms and expanding the risk of adverse events (e.g., functional decline). These infection control policies had a cascade of negative effects on mood, cognitive status, physical function, and quality of life among NH residents and staff; and were emotionally traumatic for families and others who could not visit their family member living with dementia in person.³²⁻³⁸ Yet, there is a need to evaluate the best approaches to provide dementia care, given heightened infection control policies.

Despite national initiatives (pre-COVID-19) to reduce off-label medication for these residents,^{4,6,11,18-23,39} there is growing concern that the use of off-label antipsychotics may yet again be on the rise to manage behavioral and psychological symptoms of dementia. Strategies that are used in NHs as part of a non-pharmacological comprehensive, multi-dimensional plan (e.g., group activities, consistent routine) may be hindered due to COVID-19-related infection control policies and staffing shortages. Thus, given the multiple challenges NHs face in trying to care for residents, manage behavioral and psychological symptoms among residents living with dementia, and control the spread of COVID-19, NHs may rely more heavily on pharmacological strategies.

Study Objectives

The initial study protocol was designed and initiated prior to the emergence of the COVID-19 pandemic. However, with the emergence of the COVID-19 pandemic, our study was modified to also include looking at the impact of the pandemic. Thus, two questions were addressed by this study: (a) is there a statistically significant difference in resident outcomes among NH residents living with dementia based on the non-pharmacological approach to dementia care? And (b) How did these non-pharmacological approaches compare after the emergence of COVID-19 when residents and staff faced social isolation, infection control policies, and staffing shortages? These questions were addressed via three aims:

Aim 1: Compare the effectiveness of two non-pharmacological approaches for dementia care (*TB and PB*) in reducing the use of antipsychotic medications and behavioral and psychological symptoms in NH residents living with dementia.

Aim 2: Determine the effectiveness of the two non-pharmacological approaches on NH residents living with dementia and staff safety and wellness.

Aim 3: Identify benefits, limitations, barriers, and facilitators of each approach from the perspectives of the NH staff and NH residents' families. This qualitative data will augment the resident-level quantitative data by more fully capturing the impact of the two approaches on resident outcomes; resident-staff, staff-family, and resident-family interactions; and staff job roles before and after the emergence of COVID-19, which will guide future implementation.

Study Design & Methods

The study was initiated in January 2018. As of March 2020, 80 NHs had been recruited, randomized and staff training delivered. The COVID-19 pandemic emerged in early March 2020. Subsequent national lockdown of NHs and leadership requests to not communicate with the NHs as they navigate the early days of the pandemic resulted in a pause on all research related communication between the study team and study sites.

As the pandemic evolved, the study team developed a plan for moving forward, which included assessing the ability for NHs to re-engage in the study. Due to the negative impact of the pandemic, 27 of the 80 NHs were unable to re-engage. The remaining 53 NHs were included in the revised study protocol. This change resulted in the original cluster randomized control trial becoming two sets of exploratory analyses differentiated by the emergence of the COVID-19 pandemic.

Exploratory quantitative analyses were conducted for 53 NHs (TB n=17, PB n=36 NHs). Primary resident-level outcomes included antipsychotic medication use, behavioral symptoms, wandering, and rejection of care, which were extracted from the Minimum Data Set and

electronic medical records. Six-month outcomes were captured prior to the emergence of COVID-19, while 12- and 18-month outcomes were after the start of the pandemic.

As a result of the COVID-19 pandemic and the significant impact it had on the study, the team bolstered the scope of the qualitative interviews from those that were originally planned. Qualitative data was collected via individual interviews with 327 NH staff (TB n=168, PB n=159) and 30 family caregivers (TB n= 13, PB n= 17) to explore their perspective of the two approaches as it relates to resident outcomes and training. Using mixed methods, quantitative and qualitative data were integrated to determine whether these sources confirm each other, provide emergent, or conflicting information.

Eligibility Criteria

Facility-level inclusion criteria required eligible NHs to (a) not have an existing dementia program targeting reduction of off-label antipsychotic medication use, (b) serve an average of >60 long-term care residents living with dementia, (c) be a CMS certified NH (e.g., conduct regularly scheduled resident assessments), and (d) comply with CMS's annual staff dementia care training requirement (i.e., 4 hours). Exclusion criteria included (a) NHs located in states that require more than four hours of dementia-specific training annually were excluded, (b) NHs that had existing dementia care programs which required staff to engage in additional training beyond the CMS minimum training requirements and more than the four hours required by the state.

Eligible NH residents included those that (a) have an existing diagnosis of ADRD or a Cognitive Function Scale score indicating Mild, Moderate, or Severe Cognitive Impairment, (b) are 65 years of age or older, and (c) are long-stay residents (>100 days). Post-acute care patients admitted for a brief stay (<100 days) and respite stay patients were excluded.

Eligible staff were employed by a participating NH and included all staff categories, (a) professional healthcare providers, including licensed staff with professional degrees, such as registered nurses, licensed practical nurses, rehabilitation practitioners (e.g., occupational [OT], physical [PT], speech therapists [SLP]), certified therapeutic recreation specialist, dieticians, (b) direct care providers such as certified nursing assistants [CNA], activities department staff, nutrition services personnel (e.g., dining services/aids); (c) ancillary support staff, including environmental services workers (e.g., maintenance, housekeeping, kitchen staff) and administrative staff (e.g., reception, billing department, medical records); and (d) administrators, including executive directors, directors of nursing.

Eligible family caregivers were the primary contact for a resident living with dementia in a participating NH (e.g., relative, spouse, partner, friend, per neighbor).

Statistical Considerations

Descriptive analyses included calculating appropriate central tendencies (e.g., mean) for each outcome variable. We examined outcomes separately before and after the emergence of COVID-19. To assess validity of randomization, we compared resident characteristics and outcomes and NH characteristics by arm for the six-month baseline period prior to training (December 16, 2018 to June 15, 2019).

We used the intention-to-treat analytic approach to conduct the exploratory quantitative analysis. A difference-in-differences analytic model was used, rather than comparing outcomes across the arms during each six-month period after the training, to account for baseline differences in resident characteristics and outcomes. The estimating equation is as follows:

$$Outcome_{ijt} = \beta_0 + post_t\beta_1 + (post_t \times TB_i)\beta_2 + X_{ij}\delta + NH_i + u_{ijt}$$

where $Outcome_{ijt}$ is a binary variable of having the outcome measure of interest for resident j residing in NH i at time t . $Post$ is an indicator for being in the follow-up period after implementation of approaches, which would be 1 for $t=1$ and 0 for $t=0$. TB is an indicator for NH i , which would be 1 if assigned to team-based approach arm and 0 if assigned to problem-based approach arm. The comparative effectiveness (treatment effect) of the team-based approach relative to the problem-based approach would be estimated with β_2 , which is the coefficient estimate of $post_t \times TB_i$ representing residents in team-based approach NHs during the respective follow-up period while accounting secular time trends ($post_t$) and time invariant characteristics of NH using nursing home fixed effects (NH_i). In addition, the model accounts for a set of individual resident characteristics including age, sex, race/ethnicity, Cognitive Function Scale, number of valid assessments resident had for outcome during period (X_{ij}). Models were analyzed using complete case analysis. Standard errors were clustered at the NH level. Linear probability models were implemented for ease of interpretation; regression coefficients and standard errors are presented in percentage point units. Robustness checks were conducted by implementing logistic regression difference-in-differences models with NH characteristics rather than NH-level fixed-effects to estimate the treatment effect. Marginal effects from the logistic models were computed to complement the linear probability regression models.⁴⁰ Finally, stratified analyses were conducted to examine whether treatment effects were different among residents with moderate to severe dementia vs. mild dementia. All analyses were conducted using Stata 14.0 (Stata, College Station, TX).

For resident-level primary and secondary outcomes, we conducted difference-in-differences analyses using baseline data and the first six months of post-implementation data (six-month outcomes; September 15, 2019 to March 14, 2020) to compare outcomes across the two study arms, prior to the emergence of the pandemic. Next, we conducted analyses of resident outcomes after the emergence of pandemic spanning post-implementation months (a) 7-12 (March 15, 2020-September 14, 2020) and (b) 13-18 (September 15, 2020-March 14, 2021) (12-month and 18-month outcomes analyses, respectively). Observations with missing resident covariates were excluded from the analyses.

For staff and resident secondary safety outcomes, we calculated the monthly rate (per 100 residents) of each outcome for each NH that submitted data each month. We averaged the

monthly measures available for each NH and then examined descriptive statistics (e.g., mean) to compare the outcomes across two arms during the first five months of implementation.

Qualitative Analysis

The objectives of the staff analyses were to explore (a) perceived barriers and facilitators surrounding the intervention approach, (b) perspectives on the training modules (e.g., adequacy, acceptability, satisfaction, burden), (c) the quality of resident-staff interactions (i.e., how staff training contributed to patient outcomes) and (d) training program recommendations for modifications (i.e., sustainability, scalability). We used a three-phase team-based rapid qualitative analysis approach.^{41,42} In phase one, interview transcripts were reviewed and summarized by domains (based on interview questions) and categories (emerging inductively) into a coding template. Phase two required reviewers to reduce, synthesize, and look for similarities and differences in the data through the use of matrices. In phase three, summary tabulation procedures occurred in which reviewers combined data (e.g., NH cases, care approaches), developing themes.⁴² We explored patterns and variations in themes within and across cases and care approaches.^{43,44}

We identified themes, patterns, and relationships that emerged from family caregivers that contextualized quantitative and qualitative staff findings.⁴⁵ Given the paucity of knowledge regarding the experiences of family caregivers of NH residents living with dementia, we used qualitative analysis, specifically a grounded theory approach, to further analyze caregiver interviews.⁴⁶⁻⁴⁸ We employed open, axial, and selective coding to understand the perceptions of family caregivers and create a data-driven conceptual model of family caregiver experiences.
^{41,42,43,44}

References

1. Long-Term Care Providers and Services Users in the United States: Data From the National Study of Long-Term Care Providers, 2013–2014 (2016).
5. U.S. Department of Health and Human Services, Office of Inspector General. Long-Term Trends of Psychotropic Drug Use in Nursing Homes (2022). <https://oig.hhs.gov/oei/reports/OEI-07-20-00500.pdf>

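### Does asking for a statistically significant difference, with four unranked primary outcomes and no decision rule, undermine an exploratory plan?

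*Combined protocol and SAP*

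**What the plan says.** Study Objectives, in the combined protocol and SAP, poses two questions. The first reads: "is there a statistically significant difference in resident outcomes among NH residents living with dementia based on the non-pharmacological approach". It names no outcome and no time point. The second asks: "How did these non-pharmacological approaches compare after the emergence of COVID-19".

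Study Design & Methods then explains that 27 of 80 homes could not re-engage and that the cluster trial turned into "two sets of exploratory analyses differentiated by the emergence of the COVID-19 pandemic". The same section repeats the label: "Exploratory quantitative analyses were conducted for 53 NHs". It also gives the outcome list: "Primary resident-level outcomes included antipsychotic medication use, behavioral symptoms, wandering, and rejection of care".

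Statistical Considerations uses the label a third time: "We used the intention-to-treat analytic approach to conduct the exploratory quantitative analysis". It defines the treatment effect as the coefficient on the period-by-arm interaction in a linear probability model with nursing-home fixed effects. On reporting it says that "regression coefficients and standard errors are presented in percentage point units". On timing it says: "For resident-level primary and secondary outcomes, we conducted difference-in-differences analyses using baseline data and the first six months of post-implementation data". The 7-12 and 13-18 month windows are analysed afterwards.

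The plan states no significance level, sidedness, confidence level, lead outcome, testing order or multiplicity adjustment.

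**The concern.** A question about statistical significance calls for a yes or a no. With four primary outcomes of equal standing, the answer depends on a rule: any one significant, one named outcome significant, or all of them. The plan gives no rule, and these rules carry very different false-positive rates. Antipsychotic use comes first both in Aim 1 and in the outcome list, but nothing gives it priority.

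What would be at stake is a claim that one care approach is better, resting on one small p-value out of four or more, in a trial that had already stepped back from a confirmatory role.

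**Working it through.** **No figure to reproduce.** The plan gives no error rate, power or sample-size calculation. The counts that can be checked agree: 80 − 27 = 53 homes, and 17 + 36 = 53.

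**Assumptions, none of them in the plan.** Each test is two-sided at 5% and holds that level. There is no true difference. The four test statistics are normal with equal correlation ρ.

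**Any one of four significant, one window.**

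- Independent outcomes: 1 − 0.95^4 = 1 − 0.8145 = 0.1855.
- Correlated outcomes: 1 − ∫ φ(s) [Φ((c − s√ρ)/√(1−ρ)) − Φ((−c − s√ρ)/√(1−ρ))]^4 ds, with c = 1.96.

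| ρ | 0 | 0.2 | 0.4 | 0.6 | 0.8 | 0.9 |
|---|---|---|---|---|---|---|
| Chance of at least one false positive | 18.5% | 18.0% | 16.6% | 14.4% | 11.4% | 9.4% |

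One named outcome would give 5%. So an any-one reading raises the rate by a factor of 1.9 (9.4/5) to 3.7 (18.5/5).

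**All three windows.** Reading the question across 4 × 3 = 12 tests gives 1 − 0.95^12 = 0.460 if independent, and about 40%, 32% and 19% at ρ = 0.3, 0.5 and 0.8. Restricting the question to the six-month window is an inference from the second question and the order of the analyses. The plan does not say it.

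**Does the nominal level hold?** A simulated clustered difference-in-differences test with 17 and 36 homes rejected in 5.4% to 6.3% of null runs, depending on how unequal the home sizes were. It assumed a mean of 80 residents per home, 20% prevalence and a 3-point home-by-period SD. At those sizes the independent any-one rate is 1 − 0.946^4 = 0.199 to 1 − 0.937^4 = 0.229. Those inputs are also outside the plan, so this shows only that the table may be slightly low.

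**What would change in the results.** Set the plan as written beside a plan whose first question asked how outcomes differ between the approaches. Both fit the same model to the same residents in the same windows. Both produce the same four coefficients and the same clustered standard errors per window. Confidence intervals follow directly from those two quantities. No estimate or standard error differs.

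**What a formal adjustment would cost.** Holm's method over four outcomes starts at 0.05/4 = 0.0125. A test with 80% power at 5% needs a mean statistic of 1.960 + 0.842 = 2.802. Against the critical value 2.498 for 0.0125, its power is Φ(0.304) = 62%. The 80% is illustrative, because the plan states no power for 53 homes.

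**The case for a change.** The strongest case for a change is that the significance question belongs to the revised plan, not to superseded text. A plan that asks for a verdict should say how the verdict is reached. Rewording one phrase is cheap. The error rates above count only one model form and leave out the logistic robustness models and the severity strata, which have no rule either.

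The textual part of this stands. The question and the exploratory label do not match, and neither the order of the outcome list nor that of Aim 1 supplies a rule.

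The step to a defect in the plan does not follow:

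- Apart from that phrase, the plan reads consistently as exploratory estimation. Exploratory analyses do not by themselves call for multiplicity control.
- A coefficient with its clustered standard error yields a test and an interval for each outcome. What is missing is only a rule for merging four results, and an exploratory report has no need to merge them.
- No win criterion or superiority statement is planned. The feared claim is something a careless reader might make.
- An adjustment introduced now could not restore prespecified error control. The text is in the past tense and its reference list includes a paper from February 2023. Holm's method would then cost power in exchange for a guarantee it could no longer give.

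**Conclusion.** This is a loose phrase in an objective, together with a decision rule that an exploratory analysis can do without. It is not an error in the estimates. An experienced analyst would report all four outcomes in each window as exploratory, give intervals from the clustered standard errors, and make no superiority claim from a single p<0.05. The plan's own labels already point that way.

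The size of the issue is the difference between 5% and about 9% to 19% for a reader who treats any one of four results in one window as a yes. That rests on an assumed two-sided 5% level that holds, and on assumed correlations from 0.9 to 0. It describes a misreading of the results and not a procedure in the plan. No change follows.

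### The analysis called intention-to-treat covers only the 53 of 80 randomised homes that could re-engage after the pandemic began, including for the six-month outcomes that preceded it

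*Combined protocol and SAP*

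**What the plan says.** Study Design & Methods reports: "As of March 2020, 80 NHs had been recruited, randomized and staff training delivered". It then says that, because of the pandemic, "27 of the 80 NHs were unable to re-engage. The remaining 53 NHs were included in the revised study protocol", and describes the cluster-randomised trial as "becoming two sets of exploratory analyses differentiated by the emergence of the COVID-19 pandemic". The same section gives the analysed set: "Exploratory quantitative analyses were conducted for 53 NHs (TB n=17, PB n=36 NHs").

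On timing, that section says "Six-month outcomes were captured prior to the emergence of COVID-19". Statistical Considerations dates the six-month window from 15 September 2019 to 14 March 2020.

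Statistical Considerations states: "We used the intention-to-treat analytic approach to conduct the exploratory quantitative analysis". The model codes each home by its assigned arm. It uses a difference-in-differences contrast and accounts for "time invariant characteristics of NH using nursing home fixed effects". A baseline check is also reported: "To assess validity of randomization, we compared resident characteristics and outcomes and NH characteristics by arm".

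The document does not define the intention-to-treat population, describe an analysis of all 80 homes, or give the number of homes randomised to each arm.

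**The concern.** An intention-to-treat label tells the reader that every randomised unit was analysed in its assigned arm. Here the units are homes, and about a third are absent. They are absent because of something that happened after randomisation and after training.

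The six-month analysis matters most, because it is the only pre-pandemic comparison of the primary resident-level outcomes. Pandemic disruption readily explains missing participation at 12 and 18 months. It does not by itself explain leaving homes out of an earlier window whose outcomes came from the Minimum Data Set and electronic records. Selecting homes on a later event means that the groups compared are no longer the groups formed by randomisation. If retained and lost homes changed differently between baseline and follow-up, the arm contrast can be biased.

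**Working it through.** **Inputs.** From Study Design & Methods: 80 homes randomised, 27 not re-engaged, 53 analysed (team-based 17, problem-based 36). From Statistical Considerations: the six-month window, the fixed effects and the label.

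**1. Reproduce the analysed set.** 80 − 27 = 53, and 17 + 36 = 53. Both agree with the stated figure, so the analysed homes are exactly the re-engaged homes.

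**2. Share left out.** 27/80 = 33.75%.

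**3. Order of events.** The six-month window closed on 14 March 2020. Study Design & Methods puts the emergence of the pandemic in early March 2020. The lockdown and the pause in communication followed, and the assessment of which homes could return came as the pandemic evolved. That assessment has no date. That it came after the window closed is an inference from this sequence, though a strong one.

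**4. Does the restriction reach the six-month outcomes?** The 53-home statement covers the exploratory quantitative analyses without exception. The preceding paragraph presents both sets of analyses, before and after the pandemic, as the result of the reduction to 53 homes. On the plain reading, it does.

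**5. Loss by arm.** Let T be the number of homes randomised to team-based care. At least 17 team-based and 36 problem-based homes were randomised, so T lies between 17 and 80 − 36 = 44. Then

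- team-based loss = (T − 17)/T
- problem-based loss = (80 − T − 36)/(80 − T) = (44 − T)/(80 − T)

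Every split below is an assumption, since the documents give none.

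| Randomised (team/problem) | Team-based loss | Problem-based loss |
|---|---|---|
| 17/63 | 0/17 = 0% | 27/63 = 42.9% |
| 20/60 | 3/20 = 15.0% | 24/60 = 40.0% |
| 26/54 | 9/26 = 34.6% | 18/54 = 33.3% |
| 30/50 | 13/30 = 43.3% | 14/50 = 28.0% |
| 40/40 | 23/40 = 57.5% | 4/40 = 10.0% |
| 44/36 | 27/44 = 61.4% | 0/36 = 0% |

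The reported figures therefore fit anything from near-equal loss to loss confined to one arm.

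**6. What the model can and cannot repair.** Home fixed effects remove differences between homes that stay constant over time. They do not remove differences in change over time between retained and lost homes, and they cannot bring back homes that are not in the data.

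**The case against.** The strongest defence is disclosure. The loss, its cause and the move to exploratory analyses are stated openly, and the reader meets the figure of 53 before the label. Homes are coded by assigned arm, so on a narrow reading intention-to-treat means only analysed as assigned, and the rest is attrition. This lessens the risk of misleading a careful reader. It does not make the label accurate, because assignment is respected only within a set selected after randomisation.

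A second defence concerns mechanism. Homes were lost through the impact of the pandemic, which followed nearly all of the six-month window, and nothing in the documents shows that a later shock tracks earlier change. This stands as a limit on the claim: bias is a possibility, not a finding.

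Several stronger readings are tempting and are not supported:

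- A reader might take 17 against 36 as proof that the team-based arm lost more homes. That follows under equal allocation, but allocation is not stated, and a 26/54 split would give nearly equal loss.
- A reader might infer that usable data for the 27 homes were discarded. The documents do not say whether their Minimum Data Set or record data could be obtained.
- A reader might say that no reason is given for the omission. A general reason is given, namely inability to re-engage because of the pandemic. What is missing is a reason specific to the six-month window.
- A reader might conclude that the descriptive safety rates, based on homes submitting data each month, use a different set of homes. Those homes may simply be a subset of the 53; the text does not settle it.

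**Conclusion.** The point holds as one of labelling and of the population analysed. An analysis that omits 27 of 80 randomised homes for a post-randomisation reason is not intention-to-treat. The exploratory status, the disclosure and the fixed effects do not supply the missing property.

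Two elements rest on reading rather than on an explicit statement: that re-engagement was assessed after 14 March 2020, and that the unqualified 53-home statement applies to the six-month outcomes. The direction and size of any bias cannot be determined from the documents. It is also unclear which homes entered the baseline check of randomisation. If only the 53 did, that check cannot speak for the randomisation of all 80.

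**What to change.** 1. **Label.** Replace intention-to-treat with *analysed as assigned among re-engaged homes*, and state that the comparison is not fully protected by randomisation.
2. **Flow by arm.** Report homes randomised, lost and analysed in each arm. State which homes enter the baseline check of randomisation and which enter the safety rates.
3. **Six-month outcomes.** Analyse all randomised homes as assigned, over the same calendar windows, wherever Minimum Data Set or record data can be obtained.
   - Define the post period by the calendar window for this analysis. Say that this departs from the plan's definition, which ties it to implementation, for any home trained late.
   - Report implementation dates by arm, and keep the 53-home analysis as a sensitivity analysis.
   - Use the intention-to-treat label only if all 80 homes are included. Otherwise give the reason for each missing home, by arm.
4. **If only baseline data can be obtained for the lost homes.** Compare lost with retained homes within each arm that lost any. Weighting for re-engagement is optional, only if numbers allow, and does not address unmeasured pandemic impact. If no data can be obtained, state this as a limitation.

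**Cost.** Items 1 and 2 are wording and one table, and should be done in any case. Item 3 means extracting existing records for residents of up to 27 more homes. The eligibility rule of more than 60 residents with dementia per home, on average, suggests possibly 1,600 or more (27 × 60 = 1,620, before the resident-level criteria). This is subject to data access, which the documents do not describe. Item 4 also depends on that access. No new enrolment or visits are needed.
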